6.0 Analysis Sets

6.1 Definition of Analysis Sets

Each of the three studies will represent a separate analysis set as detailed in [Table 3](#) below. No pooled analysis sets are defined.

Table 3. Definition of the Analysis Sets

Analysis Data Sets	Study Included	Study Population
1. Monotherapy	M14-212	Subjects who received at least one dose of venetoclax
2. Venetoclax in combination with HMA	M14-358	Subjects who received at least one dose of venetoclax
3. Venetoclax in combination with LDAC	M14-387	Subjects who received at least one dose of venetoclax

6.2 Rationale for Analysis Sets

The reason for not pooling the Studies M14-212, M14-358, and M14-387 is that the different treatment regimens (venetoclax monotherapy, venetoclax in combination with HMA, venetoclax in combination with LDAC) are expected to have different safety

profiles. Thus, it is not appropriate to pool data across these studies to assess the safety of venetoclax in combination with HMA or venetoclax in combination with LDAC.

1) Monotherapy Analysis Set

This analysis set includes AML subjects who have been treated with venetoclax in Study M14-212. This analysis dataset will be used to provide a comprehensive summary of safety of venetoclax monotherapy in AML subjects. Safety summaries will be presented for all subjects (N = 32).

2) Venetoclax in Combination with HMA Analysis Set

This analysis set includes subjects who received at least one dose of venetoclax in Study M14-358. This analysis dataset will be used to provide a comprehensive summary of safety of venetoclax in combination with HMA (azacitidine 75 mg/m² or decitabine 20 mg/m²). Safety summaries will be presented for the following nine groups:

1. venetoclax 400 mg QD + azacitidine (N = 84);
2. venetoclax 800 mg QD + azacitidine (N = 37);
3. venetoclax 1200 mg QD + azacitidine (N = 6);
4. overall of venetoclax + azacitidine (N = 127);
5. venetoclax 400 mg QD + decitabine (N = 31);
6. venetoclax 800 mg QD + decitabine (N = 37);
7. venetoclax 1200 mg QD + decitabine (N = 5);
8. overall of venetoclax + decitabine (N = 73);
9. DDI (drug-drug interaction) venetoclax 400 mg QD (N = 12).

3) Venetoclax in Combination with LDAC Analysis Set

This analysis set includes subjects who received at least one dose of venetoclax in Study M14-387. This analysis dataset will be used to provide a comprehensive summary of safety of venetoclax in combination with LDAC (20 mg/m² subcutaneously given Days 1 – 10). Patients with an antecedent history of myeloproliferative neoplasm (MPN) including polycythemia vera, myelofibrosis, essential thrombocythemia, or chronic myelogenous leukemia were excluded from the study in Study M14-387 Protocol Amendment 2 because emerging evidence suggested that patients with JAK2 mutated MPN may not benefit from treatment with venetoclax in combination with LDAC. To explore the safety of venetoclax in combination with LDAC both including and excluding those patients with a history of MPN, safety summaries will be presented for the following three groups:

1. All subjects (N = 92)
2. venetoclax 600 mg QD (N = 82)
3. venetoclax 600 mg QD without MPN (N = 78).

7.0 Statistical Methods

The methods described here apply to the analysis on the analysis sets described in Section 6.2.

7.1 Analysis Conventions

All data available in the extracted database will be used in the safety analyses.

Definition of Study Drug

Unless otherwise specified, the study drug in this document refers to

- Venetoclax (Study M14-212)
- Venetoclax and HMA (Study M14-358)

- Venetoclax and LDAC (Study M14-387)

Definition of Baseline

All baseline summary statistics and analyses will be based on characteristics prior to the initiation of any component of study drug. Unless otherwise stated, baseline for a given variable will be defined as the last value for that variable obtained prior to the first dose of any component of study drug.

Definition of Study Day

Study Day is defined as the number of days since (positive numbers) or prior to (negative numbers) the first dose of study drug. The day of the first dose of study drug is defined as Study Day 1, while the day prior to the first dose of study drug is defined as Study Day -1; there is no Study Day 0.

Definition of Final Observation

The final observation is defined as the last non-missing observation collected after the first dose of study drug to the last dose of study drug + 30 days.

7.2 Subject Disposition

The number and percentage of subjects will be provided for analysis data sets 2 – 3 specified in [Table 3](#) for the following summaries. The summary of subject disposition for Study M14-212 is in study CSR.

- Subjects by country
- Subjects discontinued for each reported primary reason (e.g., due to AE, due to disease progression, due to withdrew consent, etc.).

7.3 Study Drug Exposure

Exposure to venetoclax will be characterized in the following ways for summarization:

- Treatment duration: time from the first dose to the last dose of study drug (days)
- Treatment cycle: number of cycles that subjects are exposed to venetoclax
- Dose Intensity due to reduction: the ratio of actual total venetoclax dose and the planned total venetoclax. Days without venetoclax are not included in the planned total venetoclax dose.
- Dose Intensity due to reduction and interruption: the ratio of actual total venetoclax dose and the planned total venetoclax dose in the time period between first dose of venetoclax to the last dose of venetoclax. Days without venetoclax are included in the planned total venetoclax dose.

Dose intensity is also summarized for subjects who are moderate or strong CYP3A inhibitor users. The moderate or strong CYP3A inhibitor users are defined as subjects who take moderate or strong CYP3A inhibitors with venetoclax for a period with at least 7 days.

Exposure to LDAC and HMA will be characterized in the following ways for summarization:

- Treatment cycle: The number of cycles that subjects are exposed to LDAC or HMA

7.4 Demographics and Baseline Disease Related Characteristics

The following demographics and baseline disease related characteristics will be summarized for Analysis Data Sets 1 – 3 specified in [Table 3](#).

Demographics:

- Gender (Male, Female)
- Age (< 75 years, ≥ 75 years)
- Race (White, Non-white)

- Weight (< 75 kg, ≥ kg)
- Region (US and Non-US)

Baseline and Disease-Related Characteristics:

	Study M14-212	Study M14-358	Study M14-387
Baseline Bone Marrow Blast (%) (mean, SD, median, range)	√	√	√
Baseline Bone Marrow Blast (< 30%, 30 – 50%, ≥ 50%)	√	√	√
ECOG Performance Status (0, 1, 2, 3)	√	√	√
Subjects with secondary AML (Yes, No)		√	√
Cytogenetics (Intermediate, Poor)		√	√
AML Disease Type (Primary, Secondary)		√	√
Subjects receiving prior HMA for MDS (Yes, No)		N/A	√
Antecedent hematologic history (Yes, No)		√	√
History of oncological surgery (Yes, No)		√	√
Prior oncological therapy (Yes, No)		√	√
History of radiation therapy (Yes, No)		√	√
Transfusion independence at baseline (Yes, No)		√	√
Prior MPN (Yes, No)		√	√
Prior Hydroxyurea Use (Yes, No)		√	√
Fulfilling Modified Ferrara Criteria (Yes, No)		√	√
Comorbidities (Yes, No) if data is available		√	√

For demographic and baseline characteristics: categorical data will be summarized with the number of subjects and corresponding percentage – the number and percentage of subjects with missing information will also be summarized; continuous data will be summarized with sample size, mean, standard deviation, median, and range.

7.5 Prior and Concomitant Medications

Prior medications include all medications administered prior to the first dose of study drug. Concomitant medications include all medications administered (started treatment or continued treatment) during the treatment period defined as the day of the first dose of study drug through the day of the final dose of study drug.

The number and percentage of subjects that received at least one concomitant medication ("Any Concomitant Medication") will be summarized. Additionally, the number and percentage of subjects who received concomitant medications will be summarized by the World Health Organization (WHO) generic drug names according to the WHO-DRUG dictionary. Similar summaries will be presented for prior medications.

For summaries of concomitant medications, if an incomplete start date was collected for a medication, the medication will be assumed to be a concomitant medication unless there is evidence that confirms that the medication was not a concomitant medication (e.g., the medication end date was prior to the first dose of study drug).

A subject who reports the use of two or more medications will be counted only once in the summary of "Any Concomitant Medication." A subject who reports two or more uses of the same medication will be counted only once in the total for the associated WHO generic drug name. Similar rules apply to prior medications as well.

Concomitant medications will be summarized for analysis data sets 2 – 3 specified in [Table 3](#). The summary for prior and concomitant medications of Study M14-212 is in study CSR.

In addition, post-treatment therapy will be summarized for analysis data sets 2 – 3.

7.6 Adverse Events

All summaries/analyses involving AEs will include treatment-emergent AEs (TEAE) only, unless otherwise specified. TEAEs are defined as any event with onset or worsening after the first dose of study drug and no more than 30 days after the last dose of

study drug. If an incomplete onset date was collected for an AE, the AE will be assumed to be treatment-emergent unless there is evidence that confirms that the AE was not treatment-emergent (e.g., the AE end date was prior to the date of the first dose of study drug).

All adverse event summaries will be summarized for analysis sets 2 – 3 specified in [Table 3](#).

7.6.1 Analysis of Treatment Emergent Adverse Events

Adverse event data will be summarized using system organ classes (SOCs) and preferred terms (PTs) from the Medical Dictionary for Regulatory Activities (MedDRA) Version 21.0 or later for Studies M14-358 and M14-387. Adverse events were coded and summarized in MedDRA Version 18.1 for the Study M14-212 CSR.

For each AE summary, the number and percentage of subjects experiencing at least one AE will be presented (overall) for each dosing group. Subjects reporting more than one AE within a SOC will be counted only once for that SOC. Subjects reporting more than one AE for a PT will be counted only once for that PT.

For summaries of AEs by the National Cancer Institute Common Toxicity Criteria (NCI CTC) grade, at each level of summation (overall, SOC, and PT) each subject is counted only once at the maximum grade level. The number and percentage of subjects experiencing at least one event for each of the following events will be summarized (but not limited to):

- Any TEAE.
- Any TEAE with reasonable possibility related to venetoclax by the investigator.
- Any TEAE with NCI toxicity (CTCAE V4.0) Grade 3, 4, or 5 adverse events.
- Any TEAE with NCI toxicity (CTCAE V4.0) Grade 3 or 4 adverse event.
- Any treatment-emergent serious AE (SAE).
- Any TEAE leading to discontinuation of venetoclax.

- Any TEAE leading to venetoclax dose interruption.
- Any TEAE leading to venetoclax dose reduction.
- Any TEAE leading to hospitalizations.
- Any TEAE of special interest (AESI) (Section 7.6.2).
- Any TEAE leading to death.
- Any TEAE with reasonable possibility related to HMA (Study M14-358) or LDAC (Study M14-387) by the investigator.
- Any TEAE leading to discontinuation of HMA (Study M14-358) or LDAC (Study M14-387).
- Any TEAE leading to HMA (Study M14-358) or LDAC (Study M14-387) dose interruption.
- Any TEAE leading to HMA (Study M14-358) or LDAC (Study M14-387) dose reduction.

7.6.2 Selected Treatment-Emergent Adverse Events

The selected TEAEs will be summarized by following the search criteria [Table 4](#).

Table 4. Selected Adverse Events

Selected Adverse Events	Search Criteria
Tumor Lysis Syndrome (AE)	SMQ – "Tumor Lysis Syndrome" (narrow)
Grade \geq 3 neutropenia	PT terms – "neutropenia," "neutrophil count decreased," "febrile neutropenia," "agranulocytosis," "neutropenic infection," and "neutropenic sepsis"
Grade \geq 3 infection, including opportunistic infections	SOC of "infections and infestations"
Haemorrhages (SMQ)	SMQ – "Haemorrhages" (narrow)

AE = adverse events; PT = preferred term; SMQ = Standardised MedDRA Query; SOC = system organ class

7.6.3 Hospitalization Due to Serious Adverse Events

Hospitalization due to serious adverse events will be summarized for analysis data set 2 – 3. The number of days of hospitalization during the treatment period will be

summarized with descriptive statistics. The treatment period is defined as from the first date of study drug to 30 days after last date of study drug. This analysis will be performed for analysis dataset 2 – 3.

7.6.4 Transfusion During the Treatment Period

Transfusion during the treatment period will be summarized for analysis dataset 1 – 3. The number of transfusions for each type of transfusion (RBC and Platelet) during the treatment period will be summarized with descriptive statistics.

7.6.5 Subgroup Assessment of Adverse Events for Overall Treatment Groups

TEAE, grade 3 or above TEAEs, and SAEs, will be assessed for the subgroups defined below in analysis datasets 2 – 3.

- Gender (Male, Female)
- Age (< 75 years, ≥ 75 years)
- Race (White, Non-white)
- Geographic region (US, Non-US)
- Best response (CR, CRh, CR/CRh, non-CR/CRh)
- Baseline Weight (< 75 kg, ≥ 75 kg)
- Baseline Renal Function (Normal, Mild impairment, Moderate impairment, sever impairment)
- Baseline Hepatic Function (Normal, Mild impairment, Moderate impairment, sever impairment)
- Moderate or Strong CYP3A inhibitors Users during treatment period

Study M14-358:

1. overall of venetoclax + azacitidine (N = 127);
2. venetoclax 400 mg QD + azacitidine (N = 84);
3. overall of venetoclax + decitabine (N = 73);

Study M14-387:

1. All subjects venetoclax 600 mg QD + LDAC or venetoclax 800 mg QD + LDAC (N = 92)
2. venetoclax 600 mg QD + LDAC (N = 82)
3. venetoclax 600 mg QD + LDAC and without MPN (N = 78).

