Appendix C. Sample List of Excluded and Cautionary Medications

Excluded During Ramp-Up Phase and Throughout Study:
Strong CYP3A inducers – avasimibe, carbamazepine (Tegretol [®]), phenytoin (Dilantin [®]), enzalutamine, mitotane rifampin (Rifadin [®]), St. John's wort
Cautionary (Additional Guidance Noted in Table 1):

Moderate CYP3A inducers – bosentan, efavirenz, etravirine, modafinil, nafcillin
 
Strong CYP3A inhibitors – boceprevir, clarithromycin, cobicistat, conivaptan, danoprevir/ritonavir, elvitegravir/ritonavir, idelalisib,* indinavir, itraconazole, ketoconazole, lopinavir/ritonavir, mibefradil, nefazodone, nelfinavir, paritaprevir/ritonavir combinations posaconazole, ritonavir, saquinavir, telaprevir, telithromycin, tipranavir/ritonavir, voriconazole
 
Moderate CYP3A inhibitors – amprenavir, aprepitant, atazanavir, cimetidine, ciprofloxacin, clotrimazole, crizotinib,* cyclosporine,* darunavir/ritonavir, diltiazem, dronedarone, erythromycin, fluconazole, fluvoxamine, fosamprenavir, imatinib,* isavuconazole, tofisopam, verapamil

Cautionary:

Warfarin and Courmarin derivatives**
 
P-gp substrates Aliskiren, ambrisentan, colchicine, dabigatran etexilate, digoxin, everolimus,* fexofenadine, lapatinib,* loperamide, maraviroc, nilotinib,* ranolazine, saxagliptin, sirolimus,* sitagliptin, talinolol, tolvaptan, topotecan*
 
BCRP substrates Methotrexate,* mitoxantrone,* irinotecan,* lapatinib,* rosuvastatin, sulfasalazine, topotecan*
 
OATP1B1/1B3 substrates Atrasentan, atorvastatin, ezetimibe, fluvastatin, glyburide, rosuvastatin, pitavastatin, pravastatin, repaglinide, simvastatin acid, telmisartan, valsartan, olmesartan
 
P-gp inhibitors Amiodarone, captopril, carvedilol, felodipine, quercetin, quinidine, ronalzine, ticagrelor
 
BCRP inhibitors gefitinib*

Note that this is not an exhaustive list. For an updated list, see the following link:

<http://www.fda.gov/Drugs/DevelopmentApprovalProcess/DevelopmentResources/DrugInteractionsLabeling/ucm080499.htm>.

In addition to the medications listed in this table, subjects receiving venetoclax should not consume grapefruit, grapefruit products, Seville oranges (including marmalade containing Seville oranges) or Starfruits.

* These are anticancer agents; consult contact the AbbVie medical monitor before use.

** Closely monitor the international normalized ratio (INR).

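### Adverse-event tables split by on-treatment CYP3A-inhibitor use and by best response use crude percentages, so event timing and length of exposure can look like differences in risk

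*SAP*

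**What the plan says.** Safety SAP 7.6.5 states that "TEAE, grade 3 or above TEAEs, and SAEs, will be assessed for the subgroups defined below in analysis datasets 2 – 3". Most of the listed factors are demographic, regional or baseline. Two are not: "Best response (CR, CRh, CR/CRh, non-CR/CRh") and "Moderate or Strong CYP3A inhibitors Users during treatment period".

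Four rules determine what those two tables will contain.

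- **Who is a user.** The only definition in the safety SAP is in 7.3, written for dose intensity: subjects who "take moderate or strong CYP3A inhibitors with venetoclax for a period with at least 7 days". It sets no baseline date and no landmark.
- **Which events count.** In safety SAP 7.6 the counting rule is "any event with onset or worsening after the first dose of study drug and no more than 30 days after the last dose". The window is not tied to inhibitor start or to the date of response.
- **What is reported.** Under 7.6.1, "the number and percentage of subjects experiencing at least one AE will be presented (overall) for each dosing group". Section 7.6 has no exposure-adjusted rate, landmark or time-dependent rule, and 7.6.5 names no other measure, so I read its tables as crude percentages too.
- **Who stays on drug.** The protocol synopsis continues treatment for subjects with controlled disease for up to 4 years after the last enrolment. Protocol 5.3.1.1 takes subjects with progression off the study.

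**The concern.** Both groupings depend on what happens after the first dose, and the event count does not respect that timing.

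For inhibitors there are two problems. A subject with a grade 3 infection in week 1 and an inhibitor from week 8 is counted as a user with an event. The event may also be the reason for the drug: protocol Table 1 allows inhibitors when a subject requires them, and the strong inhibitors in Appendix C include "posaconazole, ritonavir, saquinavir, telaprevir, telithromycin, tipranavir/ritonavir, voriconazole", among which are antifungal azoles. In addition, the longer a subject stays on venetoclax, the more chance there is to accumulate 7 days of an inhibitor and also to have an event.

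For best response the problem is exposure. Responders tend to stay on drug longer and so have a longer window in which to record a first event.

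At stake is how a reader interprets the only planned adverse-event tables split by inhibitor use, in a study that amended its entry rules to permit strong inhibitors. An excess among users could be taken as a harm of co-administration, or an excess among responders as a cost of response, when neither exists.

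**Working it through.** The plan gives no event rates or exposure by subgroup, so there is no stated figure to reproduce. The two illustrations below use assumed rates and durations and a true null effect. They show what the counting rules can produce, not what this trial will show.

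**A. Unequal exposure, same rate (bears on best response)**

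Inputs: a constant rate λ per month, the same in both groups (assumed); 10 against 2 months on drug (assumed); the 30-day tail from safety SAP 7.6, taken as one month, giving windows of 11 and 3 months.

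Formula: proportion with at least one event = 1 − exp(−λ × window).

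- λ = 0.10: 1 − exp(−1.10) = 66.7% against 1 − exp(−0.30) = 25.9%.
- λ = 0.05: 1 − exp(−0.55) = 42.3% against 1 − exp(−0.15) = 13.9%.

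The rate ratio is 1.0 in both cases by construction. Using 28-day cycles with window (days on drug + 30)/28, rates of 0.05 to 0.20 per cycle and treatment of 1 v 6, 2 v 6 or 2 v 10 cycles, the spurious gap runs from 15.5 points (14.2% v 29.8%, before rounding) to 43.2 points (45.9% v 89.1%).

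Direction is not fixed. If non-responders have a rate of 0.40 per month over a 3-month window and responders 0.10 over 11 months, the result is 1 − exp(−1.20) = 69.9% against 66.7%. The crude table then nearly hides a fourfold difference in rate.

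**B. Inhibitor with no effect (simulation, 400,000 subjects per scenario)**

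Assumptions: time on drug exponential with mean about 120 days; event window 30 days longer; background inhibitor start 0.10 per 28 days; 7 days of inhibitor on venetoclax needed to count as a user; a share q of first events prompts an inhibitor.

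| Event rate per 28 days | q | Users with event | Non-users with event | Gap (points) | Users' first events at or before inhibitor start |
|---|---|---|---|---|---|
| 0.05 | 0 | 32.9% | 17.7% | 15.2 | 40% |
| 0.05 | 0.2 | 36.9% | 15.8% | 21.2 | 49% |
| 0.05 | 0.5 | 41.9% | 12.5% | 29.4 | 59% |
| 0.10 | 0 | 52.7% | 31.2% | 21.6 | 44% |
| 0.10 | 0.2 | 57.4% | 28.1% | 29.3 | 53% |
| 0.10 | 0.5 | 63.0% | 22.8% | 40.2 | 63% |
| 0.20 | 0 | 74.2% | 49.8% | 24.4 | 51% |
| 0.20 | 0.2 | 78.1% | 46.2% | 31.8 | 60% |
| 0.20 | 0.5 | 82.1% | 39.4% | 42.6 | 69% |

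Gaps are taken before rounding. A gap appears even with q = 0, because longer-treated subjects are more likely to become users. When events and person-time are assigned by whether the inhibitor has started, the rate ratio is 1.00 to 1.01 in all nine scenarios, which is the truth. The simulation lets inhibitor use start at a constant rate. Use from Day 1, or as prophylaxis, would shrink the gap.

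**The case against.** Several points on the other side stand.

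- **The tables are descriptive.** Section 7.6.5 says events are assessed and names only users, with no explicit non-user level. The efficacy SAP (section 9.0) plans no formal testing. A reader might infer that the plan tests a contrast between groups; it does not. The risk is misreading percentages set side by side or against the overall figure.
- **Best response is partly handled.** Efficacy SAP 8.1.9.2 to 8.1.9.4 plans Kaplan-Meier time to first SAE hospitalization, grade 3 or above haemorrhage and grade 3 or above infection, before and after CR, CRh and CR/CRh, with censoring. The versions from first dose and from day 60 still group by eventual response. Other events, including neutropenia, are not covered, and none of these analyses is split by inhibitor use.
- **Becoming a user need not take long.** The exclusion criteria do not bar inhibitors, protocol Table 2 covers the ramp-up doses of Cohort C, and protocol 6.1.8.3 allows anti-infective prophylaxis at the investigator's discretion. For a subject on an inhibitor from the start, misclassified time is a matter of days and no event prompted the use. How much use is of this kind is unknown.
- **Top-line rates may be near the ceiling.** In the earlier monotherapy study (protocol 3.3), 28 of 32 subjects (87.5%) had grade 3 or above events and 27 of 32 (84.4%) had SAEs. That population was mostly relapsed or refractory. If rates here are similar, distortion would show less in the overall rows than in individual preferred terms.

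It is also tempting to say that this table decides the question Cohort C was set up to answer. The documents do not support that. Cohort C's primary objective is ORR (protocol 4.0), protocol 8.2 also cites the lower age limit and reduced liver and kidney function, and dedicated interaction studies inform dosing (protocol 3.0).

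None of this removes the mechanism, which follows from the SAP's own definitions, and nothing in the plan addresses it for inhibitor use.

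**Conclusion.** The concern holds as a limit on interpretation. With an any-time user definition, a window that opens at first dose, and crude percentages, events before inhibitor start or before response are credited to those groups and unequal exposure is ignored. Apparent differences can arise with no difference in risk, mainly in the grade 3 or above, SAE and preferred-term tables.

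The size is not known. The 67% against 26% and 42% against 14% rest on assumed rates and treatment lengths, and the simulated gaps of 15 to 43 points rest on assumed inhibitor uptake. A reader might infer that users and responders are bound to show an excess. The documents do not support that: protocol Appendix F lists infection, neutropenia and bleeding as events of the leukaemia itself, so non-responders may have higher rates that offset or reverse the gap.

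No primary endpoint is affected. This is an inexpensive improvement to a descriptive safety analysis.

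**What to change.** Amend safety SAP 7.6.5 as follows.

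1. Keep the crude tables, and label the inhibitor and best-response subgroups as post-baseline and descriptive.
2. State whether the 7-day user definition in 7.3 applies here.
3. For inhibitors, classify each event by whether its onset falls in inhibitor-on or inhibitor-off venetoclax time, and report events per 100 patient-months in each. Fix in advance how to treat the days just after the inhibitor stops, since protocol Table 1 has a 2 to 3 day interval before the venetoclax dose changes again.
4. For best response, add exposure-adjusted rates, split into time before and after response for responders.
5. State that confounding by indication, and by the venetoclax dose change that accompanies an inhibitor, remains. Complications of an infection that prompted the drug would still fall in inhibitor-on time.

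No new data are needed. Concomitant-medication start and end dates (protocol 5.2.3), event onset dates (6.1) and dosing records (5.3.1.1) are already collected. The cost is modest extra programming. With 92 subjects in the study, some cells will be small and the rates imprecise.
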